6.2.1.3 Neurotoxicity

Toxicity Scale for the Sensory Neuropathies Associated with Oxaliplatin Symptoms:

Grade 1	Paresthesias/dysesthesias* of short duration that resolve and do not interfere with function.
Grade 2	Paresthesias/dysesthesias* interfering with function, but not in activities of daily living (ADL)
Grade 3	Paresthesias/dysesthesias* with pain or with functional impairment that also interfere with ADL.
Grade 4	Persistent paresthesias/dysesthesias* that are disabling or life threatening.

* May be cold induced

For **grade 2 neurotoxicity** persisting between treatments: Reduce oxaliplatin by one dose level for the next cycle and for all subsequent cycles.

For **grade 3 neurotoxicity** resolving to grade 2 between treatments: Reduce oxaliplatin by one dose level for the next cycle and for all subsequent cycles.

For **recurrent grade 3 neurotoxicity** resolving to grade 2 between treatments: Reduce oxaliplatin by one additional dose level for the next cycle and for subsequent cycles. Oxaliplatin will not be reduced beyond level -3. If further dose reduction is required for neurotoxicity, oxaliplatin will be discontinued. Patients should continue to receive other protocol therapy.

For **grade 3 neurotoxicity** persisting between treatments: Discontinue oxaliplatin. Patients should continue to receive other protocol therapy.

For **grade 4 neurotoxicity**: Discontinue oxaliplatin. Patients should continue to receive other protocol therapy.

For **pharyngo-laryngeal dysesthesia**: Increase the duration of oxaliplatin infusion to 6 hours for all subsequent treatments.

6.2.1.4 Extravasation

Extravasation of oxaliplatin has been associated with necrosis; if extravasation is suspected, the infusion should be stopped and the drug administered at another site. Extravasation may be treated according to institutional guidelines.

6.3 Capecitabine and Radiation

Hematologic and Non-Hematologic Toxicity

Capecitabine will be held for any Grade 3 or 4 toxicity. After toxicity resolves to \leq grade 1, capecitabine will be resumed at 600 mg/m² BID to complete the 10 weekdays of therapy.

Capecitabine can be held a maximum of 7 days. If further grade 3 or 4 toxicity is noted at the reduced dose level, after toxicity resolves to \leq grade 1, capecitabine will be resumed at 500 mg/m² BID to complete two weeks of therapy. If the second dose reduction is not tolerated, capecitabine will be stopped. Patients will keep a capecitabine diary and will record the number of capecitabine tablets and the time that they take the tablets.

Grade 3 or 4 toxicities that are due to biliary ductal dilatation and resolved with placement of a biliary stent or with biliary stent change will not require a dose reduction of capecitabine or radiation therapy after stent placement. Therapy may be withheld for procedures like ERCP and biliary stenting, and restarted at the treating physician's discretion.

Radiation therapy will be held for Grade 3 or 4 nausea that is not well controlled with anti-emetic support, until nausea resolves to Grade 2 or less. It will then be resumed at same dose.

7 DRUG FORMULATION AND ADMINISTRATION

7.1 5-Fluorouracil (5-FU; fluorouracil; “Acrucil”)

Please refer to the package insert for complete product information.

Availability

5-FU is commercially available as a 50 mg/mL solution for injection in 10 mL, 20 mL, 50 mL and 100 mL vials.

Preparation

Inspect for precipitate; if found, agitate or gently heat in water bath. Bolus injections are prepared using undiluted drug. 46-48 hour infusion of 5-FU should be prepared for administration via ambulatory infusion pump according to the individual institution's standards. These solutions may be prepared in D5W or 0.9% NaCl. 5-FU should not be mixed in the same solution with most parenteral antiemetics.

Storage and Stability

Intact vials should be stored at room temperature and protected from light. Slight yellow discolor does not usually indicate decomposition. Stability in ambulatory pumps varies according to the pump, manufacturer of drug, concentration and diluent. Please refer to appropriate reference sources for additional information.

Administration

In this study, 5-FU is administered as a 400 mg/m² IV bolus followed by 2400 mg/m² by IV infusion over 46 to 48 hours.

Toxicity

Nausea, diarrhea, vomiting (mild); stomatitis: 5–8 days after treatment initiation; myelosuppression: granulocytopenia (9–14 days); thrombocytopenia (7–14 days); Alopecia; loss of nails; hyperpigmentation; photosensitivity; Maculopapular rash; palmar–plantar erythrodysesthesias: (42–82% receiving continuous infusion); CNS effects: cerebral ataxia (rare); Cardiotoxicity: MI, angina; asymptomatic S–T changes 68%; ocular effects: excessive lacrimation and less commonly, tear duct stenosis.

Drug Interactions

Leucovorin enhances the cytotoxicity of 5-FU by forming a more stable tertiary complex with thymidylate synthase. Concomitant administration of 5-FU with warfarin has been reported to result in increased INR/prolonged prothrombin time. Patients receiving both drugs should be followed with weekly INRs.

7.2 Leucovorin Calcium (Folinic Acid) Leucovorin Calcium (calcium folinate; citrovorumfactor; N 5-formyltetrahydrofolate; 5-formyl-FH₄; folinic acid).

Please refer to the package insert for complete product information.

Availability

Leucovorin calcium is commercially available in: 50 mg, 100 mg, 350 mg vials for reconstitution.

Storage and Stability

Intact vials should be stored at room temperature and protected from light. Solutions reconstituted with BWI are stable for at least 7 days at room temperature.

Preparation

Leucovorin may be reconstituted with Bacteriostatic Water for Injection (BWI) or with Sterile Water For Injection. Solutions should be further diluted in D5W, 0.9% NaCl or Rungers solution for infusion over two hours.

Administration

Leucovorin will be administered as a 400 mg/m² IV infusion over 2 hours (+/- 10 minutes) after oxaliplatin/irinotecan administration. Leucovorin may also be administered concurrently with oxaliplatin/irinotecan as a separate IV infusion.

Toxicity

The only adverse reactions associated with leucovorin are allergic reactions. These are extremely uncommon.

7.3 Oxaliplatin [Eloxatin]

Availability

Oxaliplatin is commercially available as an aqueous solution in vials containing 50 mg and 100 mg at a concentration of 5 mg/mL. The vials do not contain any preservative and they are intended for single use. Oxaliplatin is commercially available.

Storage and Stability

Intact vials should be stored at room temperature. Solutions diluted in D5W are stable for 6 hours at room temperature or 24 hours under refrigeration.

Preparation

The calculated dose of oxaliplatin should be diluted for infusion with 250 mL to 500 mL D5W. Oxaliplatin should not be diluted with a sodium chloride solution. Needles, syringes, catheters or

IV administration sets containing aluminum should not be used with oxaliplatin. As with other platinum compounds, contact with aluminum may result in a black precipitate.

Administration

Oxaliplatin will be administered by intravenous infusion over 120 minutes (+/- 10 minutes). Infusion time may be prolonged (up to 6 hours) in patients experiencing pharyngolaryngeal dysesthesia. Oxaliplatin is unstable in the presence of chloride or alkaline solutions. Do NOT mix or administer oxaliplatin with saline or other chloride-containing solutions. Do NOT administer other drugs or solutions in the same infusion line. Flush IV lines/catheters with Dextrose 5% in Water both before and after oxaliplatin administration.

Toxicity

The most commonly observed oxaliplatin toxicities include neurotoxicity, GI toxicity, and myelosuppression. Three neurotoxicity syndromes have been seen: acute sensory neuropathy develops within hours to 2 days after oxaliplatin administration. Symptoms include, paresthesias, dysesthesias, and hypoesthesia of the hands, feet and perioral region. Jaw spasm, abnormal tongue sensation, dysarthria, eye pain and a sensation of chest pressure have also been noted. Acute sensory neuropathy symptoms may be exacerbated by exposure to cold temperature or cold objects. Symptoms are reversible, usually resolving within 14 days and commonly recurring with further dosing. This syndrome has been observed in about 56% of patients receiving oxaliplatin with 5-FU and leucovorin. Acute pharyngolaryngeal dysesthesia is reported to occur in 1-2% of patients. This syndrome is characterized by a subjective sensation of difficulty breathing or swallowing without laryngospasm or bronchospasm or objective evidence of hypoxia. Avoidance of cold drinks, food and air is suggested in order to minimize pharyngolaryngeal dysesthesia. Antianxiety agents (e.g. lorazepam) may be used to treat pharyngolaryngeal dysesthesias once oxygen saturation has been documented to be normal. Peripheral neuropathy persisting > 14 days is characterized by paresthesias, dysesthesias, and hypoesthesia. Abnormalities in proprioception may also be seen. Symptoms of persistent neuropathy may improve upon discontinuation of oxaliplatin. Various agents have been used in an attempt to minimize neurotoxicity of oxaliplatin (e.g. carbamazepine, Mg⁺, Ca⁺⁺). Calcium and magnesium infusions appear to be beneficial in preventing neurotoxicity. Gastrointestinal toxicities include nausea, vomiting (oxaliplatin is considered to be moderately emetogenic) and diarrhea. Neutropenia is reported in 73% of patients receiving oxaliplatin with

5-FU and leucovorin (44% grade 3 or 4). Grade 3 or 4 thrombocytopenia is reported to occur in 4% of patients receiving the combination. Allergic reactions, similar to those seen with other platinum compounds, have also been observed in patients treated with oxaliplatin. Reactions range from rash to anaphylaxis. Rarely, oxaliplatin has been associated with pulmonary fibrosis, which may be fatal. Oxaliplatin should be discontinued in the presence of unexplained pulmonary symptoms (e.g. nonproductive cough, dysphagia) or pulmonary infiltrates until interstitial lung disease or pulmonary fibrosis have been ruled out. Recent reports of oxaliplatin extravasation suggest that tissue necrosis may result and that oxaliplatin should be considered a vesicant. No standard treatment exists for oxaliplatin extravasation although heat and sodium thiosulfate have both been suggested. Veno-occlusive disease (VOD) of the liver is a rare complication associated with oxaliplatin and 5-FU. Clinical manifestations of VOD include hepato-megaly, ascites, and jaundice. Histologically, VOD is characterized by diffuse damage in the centrilobular zone of the liver. Sequelae of VOD include hepatomegaly, splenomegaly, portal hypertension, and esophageal varices. A recent analysis of resected liver metastases in 153 patients indicated histological findings consistent with VOD in 6/27 patients who received 5-FU alone, 4/17 patients who received 5-FU and irinotecan, 20/27 patients who received 5-FU and oxaliplatin, and 14/16 who received 5-FU, oxaliplatin and irinotecan. The remaining 66 patients had not received chemotherapy prior to resection. There were no such findings in these patients. For more information on toxicities associated with oxaliplatin, please see the package insert.

7.4 Irinotecan (CPT-11, CAMPTOSAR®)

Availability

Irinotecan is commercially available as a 20 mg/mL solution for injection in 2 mL and 5 mL vials.

Storage and Stability

Intact vials should be stored at controlled room temperature 59° to 86° F (15° to 30° C) and when protected from light. Solutions diluted in D5W are reported to be stable for 48 hours under refrigeration and protected from light. Irinotecan solutions should not be frozen as the drug may precipitate.

Preparation

Irinotecan is diluted in 5% dextrose (D5W) 500 mL to a final concentration of 0.12 – 1.1 mg/mL.

Administration

In this study irinotecan will be administered as an IV infusion over 90 minutes (+/- 10 minutes).

Toxicities

Virtually all phase I and II studies of irinotecan have reported neutropenia and/or late diarrhea (diarrhea occurring more than 24 hours after irinotecan administration) as the dose-limiting toxicities (depending upon the schedule). Other commonly observed adverse events include nausea and vomiting, anorexia, abdominal cramping, alopecia, asthenia, lymphocytopenia, and anemia. Dehydration has occurred as a consequence of diarrhea, particularly when associated with severe vomiting. Patients may have an acute syndrome of lacrimation, diaphoresis, abdominal cramping, and diarrhea (early diarrhea) during or shortly after irinotecan administration; this syndrome is thought to be cholinergically mediated and may be treated and subsequently prevented with atropine. Sporadic cases of pulmonary toxicity, manifested as shortness of breath, nonproductive cough, and transient infiltrates on chest X-ray have been reported. Infrequent occurrences of mucositis or colitis (sometimes with gastrointestinal bleeding) have been observed. Occasionally, abnormalities of serum creatinine, hepatic enzymes, or thrombocytopenia have been observed. Further information regarding irinotecan may be obtained from the package insert.

7.5 Leucovorin

Storage

For stability of leucovorin, please refer to the leucovorin (e.g., WELLCOVORIN) Package Insert or Summary of Product Characteristics.

7.6 Capecitabine

Description: Capecitabine (Xeloda) is a fluoropyrimidine carbamate with antineoplastic activity. It is an orally administered systemic prodrug of 5'-deoxy-5-fluorouridine (5'-DFUR) that is converted to 5-fluorouracil.

Form: Capecitabine is supplied as a biconvex, oblong film-coat tablets for oral administration. Each light-peach colored tablet contains 150 mg capecitabine, and each peach colored tablet contains 500 mg capecitabine.

Storage and Stability: Store at 25° C (77° F); excursions permitted to 15° to 30° C (59° to 86° F), keep bottles or storage devices tightly closed.

Compatibility: Capecitabine and some of its metabolites are converted principally by liver enzymes (carboxylesterase and cytidine deaminase and TP in tumor tissues). At present, it is unknown whether this metabolism is likely to be influenced by other treatments or alcohol, which either induce or inhibit certain liver enzymes.

Allopurinol: Oxypurinol, a metabolite of allopurinol, can potentially interfere with 5-FU anabolism via orotate phosphoribosyltransferase. Although this was originally used as a strategy to protect normal tissues from 5-FU-associated toxicity, further laboratory studies suggested possible antagonism of the anticancer activity of 5-FU in some tumor models. If a patient is receiving allopurinol, the need for taking this medicine should be ascertained. If possible, allopurinol should be discontinued prior to starting on this regimen, and another agent substituted for it.

Sorivudine and Brivudine: A metabolite of the above two investigational antiviral agents, 5-bromovinyluracil, is a potent inhibitor of dihydropyrimidine dehydrogenase, the enzyme that catabolizes 5-FU. Patients should not receive concurrent therapy with either of these antiviral agents while receiving capecitabine. If a patient has received prior sorivudine or brivudine, then at least four weeks must elapse before the patient receives capecitabine therapy

Anticoagulants: See Warnings and Precautions Section 6.9 In a drug interaction study with single dose warfarin administration, there was a significant increase in the mean AUC of S-warfarin. The maximum observed INR value increased by 91%. This interaction is probably due to an inhibition of cytochrome P450 2C9 by capecitabine and/or its metabolites.

Phenytoin: Increased phenytoin plasma concentrations have been reported during concomitant use of Xeloda® with phenytoin, suggesting a potential interaction. Patients taking phenytoin concomitantly with Xeloda® should be regularly monitored for increased phenytoin plasma concentrations and associated clinical symptoms.

Laxatives: The use of drugs with laxative properties should be avoided.

Warnings and Precautions:

Renal Insufficiency: Patients with moderate renal impairment as measured by serum creatinine (> 1.3) at baseline require dose reduction. Patients with mild and moderate renal impairment at baseline should be carefully monitored for adverse events. Prompt interruption of therapy with subsequent dose adjustments will be made if a patient develops a grade 2 to 4 adverse event. Capecitabine is contraindicated in patients with a calculated creatinine clearance of < 30 ml/min. Creatinine level will be checked and creatinine clearance calculated on Study Day 8 for all subjects to ensure safety of continued administration of capecitabine.

Pregnancy/Nursing: Capecitabine may cause fetal harm when given to a pregnant woman. If the drug is used during pregnancy, or if the patient becomes pregnant while receiving this drug, the patient should be apprised of the potential hazard to the fetus. Women of childbearing potential should be advised to avoid becoming pregnant while receiving treatment with capecitabine. Because of the potential for serious adverse reactions in nursing infants from capecitabine, the patient will be instructed that nursing must be discontinued when receiving capecitabine therapy.

Coagulopathy: Patients receiving concomitant capecitabine and oral coumarin-derivative anticoagulant therapy should have their anticoagulant response (INR or prothrombin time) monitored frequently in order to adjust the anticoagulant dose accordingly. A clinically important Capecitabine-Warfarin drug interaction was demonstrated in a clinical pharmacology trial. Altered coagulation parameters and/or bleeding, including death, have been reported in patients taking capecitabine concomitantly with coumarin-derivative anticoagulants such as warfarin and phenprocoumon. Postmarketing reports have shown clinically significant increases in prothrombin time (PT) and INR in patients who were stabilized on anticoagulants at the time capecitabine was introduced. These events occurred within several days and up to several months after initiating capecitabine therapy and, in a few cases, within one month after stopping capecitabine. These events occurred in patients with and without liver metastases. Age greater

than 60 and a diagnosis of cancer independently predispose patients to an increased risk of coagulopathy.

Cardiotoxicity: The cardiotoxicity observed with capecitabine includes myocardial infarction/ischemia, angina, dysrhythmias, cardiac arrest, cardiac failure, sudden death, electrocardiographic changes, and cardiomyopathy. These adverse events may be more common in patients with a prior history of coronary artery disease.

This treatment is foreseen as a self-administered out-patient treatment, and in certain circumstances adverse events that could occur, such as diarrhea, or hand-foot syndrome can rapidly become serious. In the case where a patient experiences any toxicity between scheduled visits, the patient will be instructed to contact the clinic as soon as possible, for further directions, discontinuation of study medication, and/or treatment.

Handling: Qualified personnel, familiar with procedures that minimize undue exposure to themselves and the environment, should undertake the preparation, handling, and safe disposal of capecitabine in a self-contained and protective environment.

Availability: Capecitabine is commercially available and will not be provided free of charge by the study. It is expected that the study participants or their insurers will be responsible for the cost of Capecitabine.

Preparation

N/A- Capecitabine comes in tablet formulation

Administration

Tablets should be swallowed with water 30 minutes after the end of a meal (breakfast and dinner). If necessary, tablets may be crushed.

Ordering

Capecitabine will be prescribed by the treating medical oncologist; prescriptions will be filled by the study participants at their pharmacy of choice.

Accountability

N/A drug is not study supplied.

Destruction and Return

N/A drug is not study supplied.

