3 ELIGIBILITY CRITERIA

3.1 Inclusion Criteria:

Participants must meet the following criteria on screening examination to be eligible to participate in the study:

- 3.1.1** Cytologic or histologic proof pancreatic ductal carcinoma is required prior to study entry. Diagnosis must be confirmed by the MGH pathology department.
- 3.1.2** No evidence of metastatic disease as determined by chest CT scan, abdomen/pelvis CT scan (or MRI with gadolinium and/or manganese) within six weeks of study entry. All patients must be staged with a physical exam, chest CT, abdominal CT with intravenous contrast (or Abd MRI with gadolinium and/or manganese).
- 3.1.3** Staging laparoscopy is not required at the outset of the trial, including in patients who might otherwise receive staging laparoscopy per NCCN guidelines (high-risk body and tail lesions), because patients will receive systemic chemotherapy at equivalent dose to patients who have documented Stage IV disease.
- 3.1.4** Patients who are deemed ‘borderline resectable’ will be included. Borderline resectable is defined by the NCCN as tumors with venous involvement of the SMV/portal vein demonstrating tumor abutment with or without impingement and narrowing of the lumen, either tumor thrombus or encasement but with suitable vessel proximal and distal to the area of vessel involvement, allowing for safe resection or reconstruction; gastroduodenal artery encasement up to the hepatic artery with either short segment encasement or direct abutment of the hepatic artery, without extension to the celiac axis; or tumor abutment of the SMA not to exceed greater than 180 degrees of the circumference of the vessel wall. Tumors involving retroperitoneal structures that can be surgically removed (ie. kidney), will also be included.
- 3.1.5** Patients must be 18 years old or older. There will be no upper age restriction.
- 3.1.6** Patients with ECOG-Performance Status of 0 or 1 are eligible.

3.1.7 Life expectancy of greater than 3 months.

3.1.8 Lab Values within one week of study entry:

ANC \geq 1000 cells/mm³

Platelet count at least 100,000 cells/mm³.

AST and ALT \leq 2.5 x upper limit of normal, OR two consecutive downtrending values for patients who have undergone biliary stenting.

Total Bilirubin \leq 1.5 x upper limit of normal,

OR, for patients who have undergone biliary stenting, Total bilirubin \leq 2.0 OR two downtrending values

Serum Creatinine \leq 1.5 mg/dl

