Creatinine Clearance \geq 30ml/min (*as estimated by Cockcroft Gault Equation*):

Creatinine clearance for males =

$$\frac{(140 - \text{age [yrs]}) (\text{body wt [kg]})}{(72) (\text{serum creatinine [mg/dL]})}$$

Creatinine clearance for females = 0.85 x male value

3.1.9 The effects of radiation on the developing human fetus are known to be teratogenic.

Women of child-bearing potential and men must agree to use adequate contraception (hormonal or barrier method of birth control; abstinence) prior to study entry and for the duration of study participation plus 30 days from the last date of study drug administration. Should a woman become pregnant or suspect she is pregnant while participating in this study, she should inform her treating physician immediately.

3.1.10 The mutational analysis (SNaPSHOT panel) requires a paraffin-embedded block or ten unstained slides from the untreated biopsy specimen obtained at the time of upper endoscopy or initial diagnostic biopsy. Patients without sufficient material for SNaPSHOT will NOT be excluded from the study as this constitutes a secondary, exploratory aim of the study.

3.1.11 Ability to understand and the willingness to sign a written informed consent document.

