5.2 Agent Administration

Study participants will receive up to 8 cycles of FOLFIRINOX as indicated in the study schema. All treatments shall be administered according to institutional standard of care.

5.2.1 5-Fluorouracil: 5-FU will be administered at a dose of 400 mg/m² push per institutional standard on day one, followed by a 1200 mg/M²/d by continuous

infusion via an ambulatory infusion pump for the subsequent two days. 5-Fluorouracil is not a vesicant or irritant. Initial dose of 5-FU may be reduced if necessary; then gradually increased to full dose if tolerated. All dose adjustments are to be made at the discretion of the treating medical oncologist.

5.2.2 Oxaliplatin: Oxaliplatin will be administered as a dose of 85 mg/m² by intravenous infusion over 120 minutes. Infusion time may be prolonged (up to 6 hours) in patients experiencing pharyngolaryngeal dysesthesia. Oxaliplatin is unstable in the presence of chloride or alkaline solutions. Do NOT mix or administer oxaliplatin with saline or other chloride-containing solutions. Do NOT administer other drugs or solutions in the same infusion line. Flush IV lines/catheters with Dextrose 5% in Water both before and after oxaliplatin administration. Initial dose of Oxaliplatin may be reduced if necessary; then gradually increased to full dose if tolerated. All dose adjustments are to be made at the discretion of the treating medical oncologist.

5.2.3 Leucovorin: Leucovorin (400 mg/m²) will be diluted with 5% dextrose and administered concurrently (in separate containers using a Y-type administration set) by IV infusion over 2 hours.

5.2.4 Irinotecan: In this study irinotecan will be administered as a dose of 180 mg/m² by intravenous infusion over 90 minutes. Initial dose of Irinotecan may be reduced if necessary; then gradually increased to full dose if tolerated. All dose adjustments are to be made at the discretion of the treating medical oncologist.

5.2.5 Capecitabine: The dose of capecitabine will be given orally 825 mg/m² BID (total 1650 mg/m² per day) for a total of 10 days M-F during the week of, and the week after, proton beam radiation; or the two weeks of photon radiation. The dose of capecitabine will be fixed unless there are dose level reductions. The daily dose will be administered in two divided doses approximately 12 hours apart. The medication should be given

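### Section 7.6 requires a lower capecitabine dose when baseline creatinine exceeds 1.3, but gives no level or time point, and Sections 5.2.5 and 6.3 do not carry the rule

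*Combined protocol and SAP*

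**What the plan says.** Four parts of the combined protocol bear on this.

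- **Section 7.6, Renal Insufficiency.** "Patients with moderate renal impairment as measured by serum creatinine (> 1.3) at baseline require dose reduction". The paragraph continues: "Patients with mild and moderate renal impairment at baseline should be carefully monitored for adverse events", and then: "Prompt interruption of therapy with subsequent dose adjustments will be made if a patient develops a grade 2 to 4 adverse event". It also contraindicates the drug below a clearance of 30 ml/min and asks for a creatinine and clearance check on Day 8.
- **Section 3.1.8.** Serum creatinine up to 1.5 mg/dl is eligible, provided the Cockcroft-Gault clearance is at least 30 ml/min.
- **Section 5.2.5.** The dose is 825 mg/m² twice daily for 10 weekdays, read from a chart by body surface area. "The dose of capecitabine will be fixed unless there are dose level reductions". The section also leaves dose adjustments to the treating investigator.
- **Section 6.3.** "Capecitabine will be held for any Grade 3 or 4 toxicity". Treatment then resumes at 600 mg/m² twice daily, and at 500 mg/m² after a further grade 3 or 4 toxicity.

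**The concern.** The requirement to reduce sits in the drug-information section, while the dose is prescribed from 5.2.5 and modified under 6.3. Neither of those sections mentions creatinine, clearance or 7.6. The opening of Section 5 sends the reader to Section 6 for dose modifications of FOLFIRINOX and radiation, and nothing there leads on to 7.6. A prescriber who follows 5.2.5 and 6.3 as written would give the charted dose to a patient for whom the same protocol requires less. A prescriber who does find 7.6 is not told what to give.

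What is at stake is mainly patient safety and consistent conduct. Toxicity is also a secondary objective (1.3.3), summarised over everyone who begins treatment (14.4). For the renal subgroup, the capecitabine part of that summary could depend on which section each prescriber followed.

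**Working it through.** There is no figure in the plan to reproduce. The check is a comparison of text, plus a test of whether the affected group can exist.

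**Step 1. Side by side.**

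| Question | Section 7.6 | Sections 5.2.5 and 6.3 |
|---|---|---|
| Starting dose, creatinine above 1.3 | Reduction required; amount not given | 825 mg/m² twice daily by body surface area; no renal entry |
| Defined reduced levels | None | 600, then 500 mg/m² twice daily, each after grade 3 or 4 toxicity |
| Toxicity grade that interrupts treatment | 2 to 4 | 3 or 4 |
| Cause-specific exceptions | Renal impairment | Biliary dilatation only (6.3) |

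Section 6.3 does make an exception by cause, for toxicity due to biliary duct dilatation. So it is the natural place for a renal exception, and it has none.

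**Step 2. Is a renal adjustment built into the chart?** Dividing each charted dose by its body surface area gives a lowest value of 1000/1.3 = 769 mg/m² and a highest of 1000/1.1 = 909 mg/m². This spread around 825 is tablet rounding. No renal adjustment is hidden in it.

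**Step 3. Can a patient be above 1.3 and still eligible?** The formula in 3.1.8 is (140 − age) × weight / (72 × creatinine), multiplied by 0.85 for women. I assume that the 1.3 in 7.6 is in mg/dl, as in 3.1.8. Ages and weights are also my assumptions.

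| Patient | Creatinine 1.31 | Creatinine 1.4 | Creatinine 1.5 |
|---|---|---|---|
| Man, 65 years, 70 kg | 75×70/(72×1.31) = 55.7 | 52.1 | 48.6 |
| Woman, 65 years, 70 kg | 0.85×55.7 = 47.3 | 44.3 | 41.3 |
| Woman, 75 years, 50 kg | 29.3 | 27.4 | 25.6 |

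I used a grid of ages 50, 65, 75 and 85, weights 50, 70 and 90 kg, both sexes and these three creatinine values, which is 72 combinations. Clearance runs from 25.5 to 85.9 ml/min in men and from 21.6 to 73.0 in women. Ten combinations fall below 30, all at 50 kg, and the other 62 pass. These counts describe the formula, not the prevalence of such patients. They show that the group above 1.3 and up to 1.5 mg/dl at entry is not empty by construction.

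**Step 4. Which baseline?** Up to eight 14-day FOLFIRINOX cycles, 8 × 14 = 112 days without delays, separate entry from chemoradiation. The study calendar measures creatinine before study and again on chemoradiation days 1, 8 and 15. The word baseline in 7.6 could mean either time, and the two values need not agree.

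**The case against.** The strongest reply is that the sections can all be obeyed at once. Section 5.2.5 gives the general dose and 7.6 adds a precaution for a subgroup. The clause on dose-level reductions and the clause on investigator discretion let the prescriber follow 7.6 without breaching 5.2.5. This is partly right. A reader might infer that the protocol forces full dose on every patient until grade 3 or 4 toxicity occurs. It does not, because a reduction is permitted. But permission does not carry out a requirement. No level is named, and two investigators could treat identical patients differently with both complying with 5.2.5.

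A second reply is that 7.6 is generic label text. Some of it looks so: its anticoagulant entry cites a Section 6.9, while this protocol's Section 6 ends at 6.3. The renal paragraph is different. Its limit of 30 ml/min matches 3.1.8, and its Day 8 check for all subjects has a counterpart in the study calendar.

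Third, a reader might infer that the grade 2 rule applies to all patients and so contradicts 6.3 throughout. The text does not establish that. The sentence follows one about mild and moderate renal impairment and may cover only those patients. The conflict with 6.3 is certain for them and depends on the reading for anyone else.

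Fourth, a reader might infer that eligibility itself conflicts with 7.6. It does not, since needing a lower dose is no reason for exclusion.

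Finally, the exposure is short (10 weekdays), laboratory checks are scheduled, and patients are told to call about toxicity between visits. These limit the harm but do not settle the starting dose.

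**Conclusion.** The inconsistency stands. Section 7.6 requires a baseline reduction above 1.3 that 5.2.5 and 6.3 neither mention nor define, and it sets an interruption grade for at least the renally impaired patients that 6.3 does not share. The first part is the firmer. It rests only on reading 1.3 as mg/dl.

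The number of patients affected is not known from the documents. Arithmetically, each 2% of patients in the group is one of the 50 planned (0.02 × 50 = 1), but the plan gives no share to apply. A reader might count those between 1.3 and 1.5 mg/dl at the start of chemoradiation. The documents do not support that either: 1.5 is an entry limit and is not stated again at that point.

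The primary analysis is unaffected. The R0 resection rule and its denominator of all patients who begin the preoperative regimen do not depend on the capecitabine dose rule.

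**What to change.** Reconcile Sections 5.2.5, 6.3 and 7.6 so that one renal rule applies. It should state the threshold and its unit, the time point meant by baseline, the starting level, the toxicity grade for holding, and which patients it covers, all as the investigators decide. Refer to it from 5.2.5 and 6.3. Alternatively, remove it from 7.6 and give the reason. Section 3.1.8 can stay as it is. This review takes no position on which dose or hold rule is right.

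The cost is amendment wording. No new tests are needed, because creatinine and clearance are already scheduled before study and on chemoradiation days 1, 8 and 15. Sample size and analysis do not change.
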